This study is a Phase II controlled clinical trial that will obtain comprehensive, serial assessments of respiratory muscle strength and architecture to understand the evolution of ventilator-induced respiratory muscle weakness in critically ill children, and test whether a novel computer-based approach (Real-time Effort Driven ventilator management (REDvent)) can preserve respiratory muscle strength and reduce time on MV. REDvent offers systematic recommendations to reduce controlled ventilation during the acute phase of MV, and uses real-time measures from esophageal manometry to adjust supported ventilator pressures such that patient effort of breathing remains in a normal range during the ventilator weaning phase. This phase II clinical trial is expected to enroll 276 children with pulmonary parenchymal disease, anticipated to be ventilated > 48 hrs. Patients will be randomized to REDvent-acute vs. usual care for the acute phase of MV (interval from intubation to first spontaneous breathing trial (SBT)). Patients in either group who fail their first Spontaneous Breathing Trial (SBT), will also be randomized to REDvent-weaning vs. usual care for the weaning phase of MV (interval from first SBT to passing SBT). The primary clinical outcome is length of weaning (time from first SBT until successful passage of an SBT or extubation (whichever comes first)). Mechanistic outcomes surround multi-modal serial measures of respiratory muscle capacity (PiMax), load (resistance, compliance), effort (esophageal manometry), and architecture (ultrasound) throughout the course of MV. Upon completion, this study will provide important information on the pathogenesis and timing of respiratory muscle weakness during MV in children and whether this weakness can be mitigated by promoting more normal patient effort during MV via the use of REDvent. This will form the basis for a larger, Phase III multi-center study, powered for key clinical outcomes such as 28-day Ventilator Free Days.

A2 Protocol Summary

Title: Real-time Effort Driven Ventilator Management (REDvent)

Phase: Phase II

Funding: NIH/NHLBI R01HL124666

Committees: Steering Committee, Institutional Data and Safety Monitoring Board

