when evaluating for readiness for ventilator liberation.²¹ These patients may have lower rates of PVA because they are not permitted to breathe spontaneously until the ARDS is largely resolved, but they may have longer length of ventilation because of the lack of spontaneous breathing. A balanced lung and diaphragm protective strategy, like what is being tested in the REDvent trial, promotes spontaneous breathing earlier during ventilation. We hypothesize that this will result in shorter time on ventilation by reducing the rates of over and under assistance myotrauma (VIDD) as well as more lung protection (VILI).^{22,24,45} However, earlier spontaneous breathing may result in a higher overall rate of PVA in REDvent versus control patients, but a different distribution of PVA subtypes. Because REDvent targets physiologic levels of respiratory effort, it is likely that the under-assistance related causes of PVA which lead to double cycling (flow undershoot/premature termination) will occur less frequently. However, the lung protective component of REDvent frequently uses a higher ventilator rate than usual care, which may make Reverse Trigger more common, with double cycling. **It is therefore highly plausible that PVA frequency and subtype may mediate the relationship between REDvent intervention and outcome (Figure 5).** It is therefore important to understand when the benefits of spontaneous breathing related to prevention of diaphragm atrophy are outweighed by any additional risks related to PVA. The analytic framework must consider these potentially competing principles. Adult data confirms associations between PVA (and its subtypes) and adverse clinical outcomes.¹²⁻¹⁶ Nevertheless, human studies have not confirmed mechanistic pathways involved, although pre-clinical data support these proposed mechanisms of injury.⁶⁴⁻⁶⁷ While this study will primarily establish associations, a mediation approach (see below) to the analysis allows for causal inference and specifically leverages the **randomized** nature of the REDvent trial. To decouple these effects, when analyzing the relationship between PVA variables and length of ventilation, we stratify or control for the time to spontaneous breathing.

[figure not shown]

Figure 6: Relationship between Asynchrony index and sarcomere disruption of the diaphragm in a rabbit model for PVA

sarcomere disruption and atrophy result in functional impairments seen in VIDD, albeit with different mechanisms.

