The REDvent study will evaluate whether the REDvent intervention results in improvement in length of mechanical ventilation (clinical outcome), as well as mechanistic outcomes (PiMax and Diaphragm Atrophy). The impact of REDvent group on time to event variables (i.e. length of ventilation) will be analyzed with competing risk regression (competing risk of death), continuous outcomes (i.e. PiMax) with linear regression, and dichotomous variables (i.e. mortality) with logistic regression. In mediation analysis we will add the PVA subtypes which are different between REDvent and control patients to multivariable models. The PVA subtype will be considered a mediator if it changes the parameter estimate of the REDvent intervention by more than 20%. If the PVA subtype significantly strengthens the association between REDvent intervention and outcomes, then therapeutic trials which seek to decrease that PVA subtype may be beneficial (e.g Reverse Trigger). In contrast, if controlling for PVA subtype weakens the association between REDvent and outcome, then strategies to mitigate that type of PVA may be more harmful (e.g. Flow Undershoot). This approach allows us to simultaneously evaluate the potential benefits of a lung and diaphragm protective strategy and understand the extent to which PVA subtypes which are different between intervention and control groups affects outcomes. This type of causal inference analysis is possible because of the randomized nature of the REDvent trial in which the intervention is likely to affect PVA rates and subtypes.

Sample Size and Power: We anticipate 235 patients available for analysis, with a median time from first day of spontaneous breathing to extubation of 4 days. Using a proposed mediation analysis with a conservative estimate for a partial “r” of 0.3 of the PVA variable with the mediator outcome, a partial “r” of 0.3 for the mediator outcome with the clinical variable, then we would have a power of 0.84 to detect the overall effect estimate in the mediation model.

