Univariable analysis will focus on the relationship between the PVA variables above and clinical and mechanistic outcomes. Nearly all the variables of interest are continuous, so analyses will focus on strength of association and dose response. Nonparametric or parametric correlations will explore the relationships between continuous variables. The primary clinical outcome of length of ventilation after the first day of spontaneous breathing will be modelled with a competing risk regression to look at time to extubation against the competing risk of death. This type of model is necessary rather than traditional survival analysis or linear regression because both death and prolonged ventilation are undesired outcomes, and some proportion of children (likely 5-10%) will die even after the first day of spontaneous breathing. We have successfully used this framework in previous investigations.⁶⁸⁻⁷² We will then add in variables which may confound the relationship between PVA and clinical outcomes including demographic factors (age, co-morbidities), severity of initial lung injury, diagnostic data and medications. Similar analyses will be repeated all clinical and mechanistic outcomes. For mechanistic analysis (table 2), within each of the proposed mechanisms (VILI, VIDD, Delirium), the variable with the strongest association with PVA (or its subtype) will be included as the outcome variable.

Specific Aim 3) To develop and test a clinical decision support system using machine learning techniques to automatically identify common forms of PVA in children.

Hypothesis: (a) Machine learning models using waveforms available on all mechanical ventilators will accurately identify PVA subtypes compared to gold standard annotations which include measures of neural drive. (b) Algorithms can be optimized for high sensitivity and low false alert rates to identify children with frequent PVA.

Preliminary Data

Machine learning methods can detect DC breaths and the PVA subtypes leading to DC. We have been developing a machine learning framework using Spectral Analysis with a Convolutional Neural Network to detect PVA subtypes. Details about the methods used (and intend to employ here) are described below. Preliminary models were trained on 34, validated on 13 and tested on 18 patients from the REDvent dataset.

[figure not shown]

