2. Supported on MV for pulmonary parenchymal disease (radiographic evidence of alveolar or interstitial opacifications with a clinical risk factor for lung disease e.g. pneumonia, acute respiratory distress syndrome, aspiration, etc.) with Oxygen Saturation Index (OSI= $(\text{FiO}_2 * \text{Mean Airway Pressure} * 100) / \text{SpO}_2$) ≥ 5 or Oxygenation Index (OI= $\text{FiO}_2 * \text{Mean Airway Pressure} * 100) / \text{PaO}_2$) $\geq 4^1$ AND
3. Within 72 hours of initiation of invasive MV

Exclusion Criteria

1. Contraindications to an esophageal catheter (i.e. severe mucosal bleeding, nasal encephalocele, trans-sphenoidal surgery) OR
2. Contraindications to use of Respiratory Inductance Plethysmography (RIP) bands (i.e. omphalocele, chest immobilizer or cast) OR
3. Conditions precluding diaphragm ultrasound measurement (i.e. abdominal wall defects, pregnancy) OR
4. Conditions precluding conventional methods of weaning (i.e., status asthmaticus, severe lower airway obstruction, critical airway, intracranial hypertension, Extra Corporeal Life Support (ECLS), limitation of care, severe chronic respiratory failure, spinal cord injury above lumbar region, cyanotic heart disease (unrepaired or palliated) OR
5. Primary Attending physician refusal

Randomization Strategy and Blinding

For the acute phase, subjects will be block randomized to either arm in a 1:1 allocation ratio, stratified by age group: infant (30 days -365 days), child (366 days to ≤ 8 years), and older child/ adolescent (9-18 years); and immune suppression (congenital or acquired conditions that result in marked inability to respond to antigenic stimuli). Block randomization will use random block sizes of 4, 6 and 8 within the strata above. Weaning phase randomization is block randomized by acute phase group and age, using the same methodology. Although blinding is not possible given the open label nature of the intervention, analysis will be blinded to treatment groups. Randomization schema was loaded into the central REDCAP database by the unblinded statistician. Patients were consented for the study by one of the study investigators, and randomization in the central REDCAP database was conducted by one of the research respiratory therapists or study investigators. Prior to randomization, blocking strata variables were double checked with a second member of the study team or the primary attending physician.

Statistical Analysis Plan

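### Randomising REDvent does not make the Hypothesis A asynchrony mediation causal: the asynchrony-to-outcome path is observational, and its confounders are not specified

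*Combined protocol and SAP*

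**What the plan says.** What is randomised is ventilator strategy. The protocol abstract (276-patient version) says "Patients will be randomized to REDvent-acute vs. usual care for the acute phase of MV", with a second randomisation for patients who fail the first SBT. The July 2024 SAP says "subjects will be block randomized to either arm in a 1:1 allocation ratio". Nobody is assigned to a level of asynchrony.

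The mediation step is in Section H, Specific Aim 2, Methods and Analysis Hypothesis A:

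- Model: "In mediation analysis we will add the PVA subtypes which are different between REDvent and control patients to multivariable models".
- Decision rule: "The PVA subtype will be considered a mediator if it changes the parameter estimate of the REDvent intervention by more than 20" per cent.
- Justification: "This type of causal inference analysis is possible because of the randomized nature of the REDvent trial".

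The Preliminary Data text of the same aim says "While this study will primarily establish associations, a mediation approach (see below) to the analysis allows for causal inference", and ties this to the randomised design. It also says that when PVA is related to length of ventilation, time to spontaneous breathing will be stratified on or controlled for.

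Confounders of PVA and outcome appear only under Hypothesis B: "We will then add in variables which may confound the relationship between PVA and clinical outcomes". The list there is age, co-morbidities, severity of initial lung injury, diagnostic data and medications. Hypothesis A has no such list, states no assumption about unmeasured confounding, and plans no sensitivity analysis for it.

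**The concern.** A mediation claim needs three links: REDvent to PVA, REDvent to outcome, and PVA to outcome. Random allocation supports the first two. The third compares patients who happened to have more or less asynchrony, so anything that drives both asynchrony and outcome can distort it. The distortion also reaches the REDvent coefficient, because the model conditions on a variable measured after randomisation.

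The protocol recognises that such factors exist. Hypothesis B lists confounders, and it changes its primary outcome because the relation between PVA and length of ventilation is confounded by time to first spontaneous breathing. Hypothesis A still uses length of ventilation. Asynchrony Specific Aim 1 names respiratory drive as a source of risk for double cycling, yet drive is not on the Hypothesis B list.

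Hypothesis A turns the direction of the coefficient change into guidance. If adding a subtype strengthens the REDvent association, trials to reduce that subtype may help; if it weakens the association, reducing that subtype may harm. A change caused by confounding could point later paediatric trials at the wrong target.

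**Working it through.** **Inputs from the documents.** n = 235, 1:1 allocation, mediator declared if the REDvent estimate changes by more than 20%. The aim's stated power is 0.84 with both partial correlations at 0.3.

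**The plan's own power figure.** At n = 235 and two-sided 0.05 (assumed, since Section H gives no alpha), joint significance of both paths has power 0.994, and the Sobel test has 0.91-0.93 analytically. A value near 0.84 appears only with unstated inputs, for example joint significance at n = 120 (0.842). The test and alpha are not given, so 0.84 is not shown to be wrong, and nothing below depends on it.

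**Assumptions, not in the documents.** PVA is scaled to SD 1 within arm, and outcome likewise. REDvent shifts PVA by *a* = 0.4 to 0.6 SD. The total REDvent effect on outcome is *c* = 0.3 to 0.4 SD in size. PVA has no effect on outcome. One unadjusted common cause has standardised effect *g* on PVA and *h* on outcome, with g = h = 0.3, 0.4 or 0.5.

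**Bias in a linear model.**

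- False PVA slope = g × h = 0.09, 0.16, 0.25.
- Movement of the REDvent coefficient = a × g × h.
- Movement as a share of the total effect = a × g × h / c.

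| g = h | a = 0.4, c = 0.4 | a = 0.6, c = 0.4 | a = 0.6, c = 0.3 |
|---|---|---|---|
| 0.3 | 0.036/0.4 = 9% | 0.054/0.4 = 14% | 0.054/0.3 = 18% |
| 0.4 | 0.064/0.4 = 16% | 0.096/0.4 = 24% | 0.096/0.3 = 32% |
| 0.5 | 0.100/0.4 = 25% | 0.150/0.4 = 38% | 0.150/0.3 = 50% |

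None of these terms contains n, so more patients do not remove the bias.

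**The 20% rule applied to simulated trials** (n = 235, PVA inert, a and c over the ranges above):

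| Common cause | Trials declaring a mediator |
|---|---|
| none | 4-20% |
| 0.3 | 13-43% |
| 0.4 | 34-77% |
| 0.5 | 65-96% |

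The top row is the rule's own false-positive rate: a fixed percentage change carries no error control.

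**Effect of adjustment.** With c = 0.4, a = 0.6 and strength 0.4, full adjustment for the common cause lowers the rate from 61% to 9%. In a similar setting (a = 0.63), adjusting for a proxy of half reliability leaves 30%, against 64% unadjusted and 10% with full adjustment. Measured covariates therefore help but cannot be assumed to settle the matter.

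**A different quantity.** The standard error of the PVA slope is about 1/√235 = 0.065. False slopes of 0.09, 0.16 and 0.25 are then nominally significant in about 28%, 69% and 97% of trials. That is not the plan's rule and should not be read as its error rate.

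**The case against.** The strongest defence is that the plan does not claim as much as it seems to. The Preliminary Data sentence opens by saying that the study mainly establishes associations. The Hypothesis A sentence continues by noting that the intervention is likely to change PVA, and can be read as saying that randomisation makes the analysis possible, not that it is sufficient. The guidance to later trials is worded with may. The models are described as multivariable, control for time to spontaneous breathing is mentioned within the aim, and the July 2024 SAP adjusts all primary and secondary outcomes for age category, immunosuppression and imbalanced baseline variables, with oxygenation index added for PiMax.

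Much of this stands against a stronger reading. A reader might infer that the analysis makes no adjustment at all; the documents show incomplete specification instead. A reader might also infer that false mediation is certain to be reported. It is not: crossing 20% depends on the strength of the confounder, and confounding of opposite sign can hide a real effect.

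The defence does not close the gap. The hedge on associations is followed by an exception for mediation. The SAP does not say that its adjustments carry into Section H, and blocking or imbalanced baseline variables address treatment-group imbalance, not common causes of PVA and outcome. The control for time to spontaneous breathing is not written into the Hypothesis A models and would not cover severity or drive.

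**Conclusion.** The concern holds as a fault in the stated justification and in the specification of Hypothesis A. Randomisation identifies the REDvent effects on PVA and on outcome. The PVA-to-outcome and mediated effects also need an assumption of no unmeasured PVA-outcome confounding, which the plan neither states nor tests.

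The size depends on assumed effects. Over the ranges used, the 20% rule names an inert subtype as a mediator in 13-43%, 34-77% and 65-96% of trials at common-cause strengths 0.3, 0.4 and 0.5, against 4-20% with none. The simulations are linear, so they bear most directly on continuous outcomes such as PiMax. Length of ventilation uses competing-risk regression and mortality uses logistic regression, where the sizes may differ.

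The links in the Preliminary Data between reverse trigger and opioid dose, and between double cycling and delirium, might be taken as proof that sedation and delirium are common causes. The documents do not support that: Table 2 of Section H lists delirium scores and cumulative sedatives as possible consequences of PVA, and the text leaves the direction open for delirium.

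This is worth correcting, but it concerns a separately funded secondary analysis and has no bearing on the trial's primary conclusion.

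**What to change.** In Section H, Specific Aim 2, Hypothesis A:

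1. Adjust every mediation model for the pre-randomisation confounders already listed under Hypothesis B (age, co-morbidities, severity of initial lung injury, diagnosis, baseline medications) and for the blocking variables. Do not add time to first spontaneous breathing, sedation or respiratory drive as ordinary covariates. They follow randomisation and REDvent may change them, so adjusting for them could remove part of the REDvent effect itself. Handle them only in a sensitivity analysis or with a method suited to confounders affected by treatment.
2. State the assumption of no unmeasured PVA-outcome confounding, and add a sensitivity analysis showing how strong such a confounder would have to be to remove the indirect effect.
3. Replace the causal sentence, and its counterpart in the Preliminary Data, by a statement that randomisation protects only the REDvent effects, and that the PVA-outcome and mediated effects depend on the assumption in item 2.

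The cost is a little more analysis, on data already collected or planned, and a weaker causal claim.

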Specific Aim 2: To determine if a ventilator strategy in children with ARDS that promotes spontaneous breathing and physiologic levels of patient effort results in different rates and subtypes of PVA, and if PVA mediates the relationship between this intervention and clinical or mechanistic outcomes. **Hypothesis:** (a) REDvent intervention patients will have a different distribution of PVA subtypes than usual care patients which will partially mediate the relationship between REDvent intervention and outcome. (b) PVA subtypes which lead to DC breaths will be associated with clinical and mechanistic outcomes. **Study Design:** Secondary analysis of waveforms and clinical data from the REDvent clinical trial.

Preliminary Data

The relationship between PVA and clinical outcomes is complex because PVA is more likely to occur in patients with more spontaneous breathing. A conventional ventilator management strategy for patients with ARDS promotes controlled ventilation with high degrees of sedation or neuromuscular blockade with low rates of spontaneous breathing early during ventilation, followed by spontaneous breathing

[figure not shown]

Figure 5:
Conceptual model for Aim 2

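### The 0.84 power given under Asynchrony Aim 2, Hypothesis A leaves out the REDvent-to-PVA path, and its stated inputs alone do not yield 0.84

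*Combined protocol and SAP*

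**What the plan says.** All of this is in section H of the amended protocol, under Asynchrony Specific Aim 2.

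- **The hypothesis.** Hypothesis A predicts a "different distribution of PVA subtypes than usual care patients which will partially mediate the relationship between REDvent intervention and outcome". REDvent is the exposure and the PVA subtype is the mediator.
- **The analysis.** Under Methods and Analysis Hypothesis A, PVA rates are compared between arms by Mann-Whitney U test, and only subtypes that differ are considered for mediation. Then: "In mediation analysis we will add the PVA subtypes which are different between REDvent and control patients to multivariable models". A subtype counts as a mediator if adding it moves the REDvent coefficient by more than 20%.
- **The power statement.** Under Sample Size and Power: "We anticipate 235 patients available for analysis". The inputs are a partial r of "0.3 of the PVA variable with the mediator outcome" and a partial r of "0.3 for the mediator outcome with the clinical variable". The conclusion is "then we would have a power of 0.84 to detect the overall effect estimate in the mediation model".
- **Table 2 of section H.** It lists PVA subtypes as the variables of interest, with mechanistic measures such as PiMax, diaphragm thickness and delirium score as the mediation variables to be investigated.

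The power paragraph states no alpha, sidedness, test or direct effect. It does not say whether the overall effect is the indirect or the total effect.

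**The concern.** The chain that is powered is not the chain that is tested. Hypothesis A runs REDvent → PVA → outcome. The power inputs run PVA → mediator → clinical variable, as Table 2 does. The first link of Hypothesis A is the difference in PVA between arms, on which the rest of the analysis depends. It has no assumed effect size and no stated power.

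The figure also cannot be reproduced from what is written. The plan intends to draw conclusions about which PVA subtypes later trials should try to reduce and which may be better left alone. A reader who took 0.84 as the power of that analysis could treat a null arm comparison, or a null mediation result, as more informative than the plan supports.

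**Working it through.** **Inputs.** From the Sample Size and Power paragraph: n = 235, path a = 0.3, path b = 0.3. Two-sided alpha of 0.05 is an assumption, borrowed from the SAP's power analysis for the primary outcome. Allocation is 1:1 (SAP, Randomization Strategy and Blinding), so about 117.5 per arm.

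**1. Trying to reproduce 0.84 as an indirect effect.**

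- Each path, Fisher z: atanh(0.3) × √232 = 0.3095 × 15.23 = 4.71. Power = Φ(4.71 − 1.96) = 0.997.
- Joint significance of both paths, noncentral t: about 0.998 × 0.998 = 0.995. Simulation gives 0.993.
- Sobel, analytic: z_a = 0.3/√0.91 × √233 = 4.80 and z_b = 0.3/√0.91 × √232 = 4.79. Then z = z_a·z_b/√(z_a² + z_b²) = 3.39, and power = Φ(3.39 − 1.96) = 0.92. Aroian's variant also gives 0.92. The simulated Sobel test gives 0.985.
- Monte Carlo product test, simulated: 0.994.

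**2. Trying to reproduce 0.84 as a total effect.** With no direct effect, r = 0.3 × 0.3 = 0.09. Then atanh(0.09) × 15.23 = 1.37, and power = Φ(1.37 − 1.96) = 0.28 (one-sided 0.39).

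**3. What does give about 0.84.** Each route adds something the plan does not state.

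| Added assumption | Power |
|---|---|
| Direct effect 0.10, so total r = 0.19 | 0.834 (Fisher z), 0.840 (noncentral t) |
| Analytic Sobel at two-sided alpha 0.05/3: Φ(3.39 − 2.39) | 0.84 |
| Analytic Sobel / Aroian at one-sided alpha 0.01 | 0.856 / 0.848 |

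**4. Power for the chain in Hypothesis A.** The documents give no arm difference in PVA, because group comparisons were still blinded. The differences below are therefore assumptions, in SD units.

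- Mann-Whitney comparison, with efficiency 0.955 relative to the two-sample z test (the value for normal data): power = Φ(d × √(117.5 × 0.955/2) − 1.96) = Φ(7.49d − 1.96).
- Joint significance: first path by two-sample z, Φ(d × √(117.5/2) − 1.96) = Φ(7.66d − 1.96), multiplied by 0.997 for a PVA-outcome partial r of 0.3.

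| Arm difference in PVA (SD) | Mann-Whitney comparison | Joint significance |
|---|---|---|
| 0.2 | 0.32 | 0.33 |
| 0.3 | 0.61 | 0.63 |
| 0.4 | 0.85 | 0.86 |
| 0.63 (equivalent to r = 0.3) | 0.997 | 0.99 |

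The joint column slightly exceeds the Mann-Whitney column only because its first path uses the z test. With Mann-Whitney as the first step, the product at the first three differences is 0.32, 0.61 and 0.85.

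The 0.3 for PVA with outcome is the plan's own value for PVA with a mechanistic variable. For a clinical outcome, the plan's two paths with no direct effect imply 0.09. Joint power could then not exceed about 0.28, whatever the arm difference.

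**The case against.** The strongest reply is that with alpha, test and direct effect unstated, 0.84 may have been correctly computed under assumptions that were left out. That stands. A reader might infer an arithmetic error, or that 0.84 arises only from a hidden direct effect of 0.10. The documents support neither. The analytic Sobel formula with no direct effect gives 0.84 at alpha 0.05/3, and the Hypothesis B methods do name three mechanisms, although no such division of alpha is written anywhere.

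A reader might also infer that 0.84 overstates power. On the indirect-effect reading it understates it (0.92 to 0.99). Only the total-effect reading with zero direct effect falls far short, and the plan does not say that reading was meant. Nor can one say that the arm comparison will fail more often than stated, since no power is stated for it. At 0.4 SD or more, joint power for the REDvent chain is 0.86 or higher.

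The paragraph may have been meant for Aim 2 as a whole: it sits between Hypotheses A and B, and Hypothesis B has no power paragraph of its own. That is possible, but as placed it follows the Hypothesis A methods with nothing to say otherwise. Reading its mediator as a mechanistic variable is an inference from Table 2, but REDvent is absent from the inputs on any reading.

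Finally, joint significance is not the planned rule. Power for a change of more than 20% in the REDvent coefficient cannot be computed from the documents, and any replacement figures must say so.

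**Conclusion.** The point holds as one of misattribution and under-specification. The 0.84 is built from a chain that starts at PVA, so it is not the power of the REDvent → PVA → outcome analysis, of the between-arm comparison that precedes it, or of the 20% rule. At an assumed two-sided alpha of 0.05, the stated inputs give 0.92 to 0.99 for the indirect effect and about 0.28 for the total effect with no direct effect. Neither reading is 0.84.

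For the chain actually hypothesised, power depends on an arm difference that the plan does not give. Joint-significance power runs from about 0.33 at 0.2 SD to 0.86 at 0.4 SD if the PVA-outcome partial r is 0.3. This is a minor point: it concerns a secondary analysis of trial data, and no sample size, primary test or stopping decision rests on it.

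**What to change.** Either remove 0.84 as the power for Hypothesis A, or relabel it as power for the PVA → mechanism → outcome chain. If it is relabelled, state alpha, test, whether the effect is indirect or total, and any direct effect, and correct the number to match.

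For Hypothesis A, add a statement such as:

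> With 235 patients (1:1) and two-sided alpha 0.05, the Mann-Whitney comparison of a PVA subtype between arms has power of about 0.32, 0.61 and 0.85 for differences of 0.2, 0.3 and 0.4 SD. If the PVA-outcome partial r is 0.3, joint-significance power for mediation is about 0.33, 0.63 and 0.86. The arm difference is an assumption, and these figures do not cover the rule based on a change of more than 20% in the estimate.

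The cost is two or three sentences, with no change to data collection, analysis or the primary sample size. The downside is a less favourable stated power if the arm difference is small.
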